#### 4.2.5.2 Anti-drug antibody (ADA)

Serum samples for ADA assessments will be conducted utilizing a tiered approach (screen, confirm, titer), and ADA data will be collected at scheduled visits shown in the CSP. ADA result from each sample will be reported as either positive or negative; samples without an ADA result will not be imputed. If the sample is positive, the ADA titer will be reported as well. In addition, the presence of neutralizing anti-drug antibody (nAb) and anti-YTE will be tested for all ADA-positive samples using validated ligand-binding assays. The nAb and anti-YTE results will be reported as positive or negative.

The number of subjects in the as-treated population and the as-treated Japan subpopulation (defined in Section 2.1) who fulfil the following the criteria will be determined. The percentage of ADA-positive subjects in each of the categories specified below will be calculated, using the number of subjects with any ADA result at baseline and/or post-baseline during the study as the denominator. A subject is defined as being ADA positive if a positive ADA result is available at any time, including baseline and all post-baseline measurements; otherwise ADA negative. Missing ADA result will not be imputed.

- ADA positive at any visit; the percentage of ADA-positive subjects is known as ADA prevalence.
- Treatment-emergent ADA defined as the sum of both treatment-induced and treatment-boosted ADA; the percentage of subjects fulfilling this criterion is known as ADA incidence.
- ADA positive at both post-baseline and baseline.
- ADA positive post-baseline and not detected at baseline (treatment-induced ADA).
- ADA not detected post-baseline and positive at baseline.
- Treatment-emergent ADA-negative, defined as ADA-positive at any visit but not fulfilling the definition of treatment-emergent ADA-positive.
- Treatment-emergent ADA positive with maximum titer higher than median of maximum titers. The median of maximum titers is calculated based on the maximum titer for each ADA-positive subject within the actual dose administered group; ‘nirsevimab 50mg/100mg’ and ‘nirsevimab 200mg’ (including both baseline and post-baseline measurements).
- Treatment-boosted ADA, defined as a baseline positive ADA titer that was boosted to a 4-fold or higher level (greater than the analytical variance of the assay) following drug administration.
- Persistently positive ADA, defined as negative at baseline and having at least 2 post-baseline ADA positive measurements with at least 16 weeks (112 days) between the first and last positive measurement or an ADA positive result at the last available assessment.
- Transiently positive ADA, defined as negative at baseline and having at least one post-baseline ADA positive measurement and not fulfilling the conditions for persistently positive.
- nAb positive at any visit (nAb prevalence).

- nAb positive post-baseline only (nAb incidence)
- anti-YTE positive at any visit (anti-YTE prevalence).
  - anti-YTE positive post-baseline only (anti-YTE incidence)

To evaluate the impact of ADA on safety, TEAE and TESAE by MedDRA SOC and PT will be summarized by ADA post-baseline status (ie, at least one post-baseline ADA positive or not through 360 days post dose).

Samples with ADA titer < 50 will be regarded as negative results and samples with ADA titer  $\leq 50$  (borderline positive) will be regarded as positive results. The evaluation on the impact of ADA on PK is described in Section 4.2.5.1.

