4.3.3.2 Antidrug Antibody Evaluation

Blood samples to evaluate ADA responses to nirsevimab in serum will be collected according to scheduled time points. Blood samples will also be collected for ADA response from subjects hospitalized with LRTI or any respiratory infection within approximately 2 days following hospitalization. See the collection schedule in Section 4.2. Evaluations will be performed using validated immunoassays.

CCI

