#### **4.2.5 Secondary analyses**

##### **4.2.5.1 Pharmacokinetics**

Nirsevimab serum concentration data for each nominal sampling time will be summarized by dose using descriptive statistics, including  $n <$  lower limit of quantification (LLOQ), geometric mean, geometric coefficient of variation (CV) (%), geometric SD, geometric mean  $\pm$  geometric SD, and the summary statistics listed in Section 4.1.1, and a listing of nirsevimab serum concentrations will also be provided. Line plot of geometric mean of nirsevimab serum concentration on log-normal scale will be plotted by scheduled visit. Geometric mean and other summary statistics are derived from planned visit day  $\pm$  14 days.

Nirsevimab serum concentration at each scheduled visit will be summarized by subject disease conditions as defined in inclusion criterion number 2, see [Appendix 4](#). The summary statistics of number of subjects, mean, SD, minimum and maximum will be provided. A series of spaghetti plots, will be created for each of the disease conditions stated in inclusion criterion number 2, presenting individual subjects nirsevimab serum concentration over time.

Individual nirsevimab serum concentrations with geometric mean  $\pm$  geometric SD will be graphically illustrated, and summarized, by ADA status (ADA positive and ADA negative). Definitions of ADA status are described in Section 0.

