**Table 1 Population for medically attend RSV respiratory illness**

Type of Endpoint	Endpoint	Protocol definition of LRTI	RSV test result	Investigators assessment of LRTI/URTI	Setting of care
Secondary Efficacy	MA RSV LRTI	Protocol defined	Positive (central RT-PCR)	LRTI	Inpatient or outpatient
Secondary Efficacy	MA RSV LRTI with hospitalization	Protocol defined	Positive (central RT-PCR)	LRTI	Inpatient

CCI

[figure not shown]
All above stated summaries will be based on observed events and data summary will be presented through 150 days post dose, after 150 days post dose, and through 360 days post dose.

Adverse events associated with all medically attended RSV LRTI will be summarized, as well as categorized by the MedDRA SOC and PT. Summaries will be presented through 150 days post dose, after 150 days post dose, and through 360 days post dose.

[figure not shown]
To evaluate the impact of ADA on efficacy, MA LRTI and MA LRTI with hospitalization will be summarized by ADA post-baseline status (ie, at least one post-baseline ADA positive or not through 360 days post dose).

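### ADA incidence is diluted by children with only a baseline result, and ADA status set by any later positive labels concentrations and events that came before it.

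*SAP*

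**What the plan says.** Protocol 2.2 makes the incidence of ADA in serum a secondary endpoint. SAP 4.2.5.2 gives one denominator for all ADA categories, "using the number of subjects with any ADA result at baseline and/or post-baseline during the study as the denominator". It defines incidence as treatment-induced plus treatment-boosted ADA. The induced part is "ADA positive post-baseline and not detected at baseline (treatment-induced ADA"; the boosted part needs a positive baseline titer and at least a four-fold rise. Persistent and transient ADA are worded differently, for example "Persistently positive ADA, defined as negative at baseline and having at least 2 post-baseline ADA positive measurements". SAP 2.1 defines no ADA-evaluable set.

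Two status variables are then used to look for an effect of ADA:

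- **Pharmacokinetics (SAP 4.2.5.1).** Individual concentrations "will be graphically illustrated, and summarized, by ADA status (ADA positive and ADA negative". Under SAP 4.2.5.2 a child is positive if any sample is positive, "including baseline and all post-baseline measurements; otherwise ADA negative".
- **Events (SAP 4.2.5.2 for TEAEs and TESAEs, 4.2.5.3 for LRTI).** "MA LRTI and MA LRTI with hospitalization will be summarized by ADA post-baseline status", and the status is "ie, at least one post-baseline ADA positive or not through 360 days post dose". The LRTI sentence names no event window.

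Scheduled ADA samples are at baseline and Days 31, 151 and 361. Protocol 4.3.3.2 adds one: "Blood samples will also be collected for ADA response from subjects hospitalized with LRTI or any respiratory infection".

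**The concern.** **Denominator.** Any-result is the natural base for prevalence. Incidence compares a post-baseline result with a baseline one, so a child with no post-baseline result adds to the denominator and can never add to the numerator. Reported incidence falls by the share of such children.

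**Timing of status.** Neither status variable is tied to the date of the concentration or event. A child who first turns positive at Day 361 has the Day 31 and Day 151 concentrations, and nearly all earlier events, placed in the ADA-positive group. If most positives are late, the Day 151 positive group consists mainly of children in whom no ADA had yet been found, and a real effect on exposure would be muted. Protocol 4.8.5 asks for the impact of ADA on PK, and protection over about five months rests on those concentrations.

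**Default to negative.** Both definitions also put a child with no post-baseline ADA result in the negative group, which matters mainly for the event splits. Status depends on completing follow-up as well: a child can be negative at a Day 151 interim analysis and be relabelled at the final one.

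**Working it through.** **Inputs from the documents**

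- Phase 1b/2a (Protocol 1.4.2): post-baseline ADA in 20/71 = 28.2%; at Day 361 only in 18/68 = 26.5%; the other two were positive at Day 50 only; none was positive at Day 151.
- Phase 2b (Protocol 1.4.3): post-baseline ADA in 52/929 = 5.6%. Anti-YTE results are given for 17 ADA-positive children at Day 151 and 30 at Day 361.
- Planned size about 100, in two dose groups of about 50 (Protocol 3.1.1).

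The printed percentages reproduce. The plan states no expected ADA incidence and no expected share of missing ADA samples.

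**1. Denominator.** Let *I* be the incidence among children with both results and *b* the share with only a baseline result (assumed). Reported incidence = *I* × (1 − *b*).

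| *b* | *I* = 5.6% | *I* = 28.2% |
|---|---|---|
| 4% | 5.38% | 27.07% |
| 10% | 5.04% | 25.38% |
| 20% | 4.48% | 22.56% |

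For scale, exact 95% intervals are 2.2% to 12.6% for 6/100 and 19.5% to 37.9% for 28/100.

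**2. Day 151 concentrations.** Let *f* be the share of ever-positive children already positive by about Day 151, and *g* an assumed true geometric mean ratio (positive to negative) at that visit. If the late positives behave like negatives, the apparent ratio is *g*^*f*.

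- Phase 1b/2a: *f* = 2/20 = 0.10. The share at Day 361 only is 18/20 = 90% (exact 95% CI 68% to 99%).
- Phase 2b: *f* ≈ 17/52 = 0.33, inferred from the anti-YTE denominators.

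| True *g* (assumed) | Apparent, *f* = 0.10 | Apparent, *f* = 0.33 |
|---|---|---|
| 0.75 | 0.97 | 0.91 |
| 0.50 | 0.93 | 0.80 |
| 0.25 | 0.87 | 0.64 |

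The Phase 2b share is rough: 52 − 17 − 30 leaves at least 5 positives unplaced. If all five were positive by Day 151, *f* = 22/52 = 0.42 and a true 0.50 would appear as 0.75.

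**3. Events.** Two forces act in opposite directions.

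- *Dilution by late positives.* For early events, an assumed risk ratio of 2 appears as 1 + *f* × (2 − 1), that is 1.10 at *f* = 0.10 and 1.33 at *f* = 0.33.
- *Extra sample at hospitalization.* Take 2/71 = 2.8% for an early sample, 18/68 = 26.5% at Day 361, independence, and no true effect. The chance of any positive is 1 − 0.972 × 0.735 = 28.5%. One more early sample makes it 1 − 0.972² × 0.735 = 30.6%. For an assumed hospitalization risk of 10% to 2%, the apparent risk ratio is 1.09 to 1.10. With 2.8% at each of Days 31 and 151, it is 1.08 to 1.09.

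**4. What by-visit classification would leave.** SAP 4.1.7 needs three observations above the quantification limit for a summary. The binomial chance of at least three children positive before Day 361:

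| Early positivity | *n* = 50 | *n* = 100 |
|---|---|---|
| 2/71 = 2.8% (Phase 1b/2a) | 17% | 54% |
| 17/929 = 1.8% (Phase 2b, inferred) | 6% | 28% |

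**The case against.** The plan shows timing elsewhere. SAP 4.1 provides by-visit ADA summaries, 4.2.5.1 a concentration listing and individual plots, and 4.2.5.2 persistent and transient categories. Parts of the exploratory section are redacted and may hold more. These displays let a reader reconstruct the order of events, but on the visible text they do not change the status used in the splits.

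The analyses are descriptive: SAP 4 plans no formal comparisons, and SAP 3.2.2 assesses ADA impact only if data permit. The two earlier infant studies reported no apparent effect of ADA on PK. That limits the consequence, and the ratios above are illustrations rather than expectations.

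Three stronger readings are tempting but not supported.

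- *A missing baseline leaves incidence undefined.* A reader might infer this because induced ADA uses not-detected wording and persistent ADA uses negative. But SAP 4.2.5.2 reports each sample as positive or negative, rules out imputation, and uses not detected as a result elsewhere in the same list. Counting a missing baseline as not detected would in effect impute a negative. What remains is an untidy wording.
- *The secondary efficacy endpoint through 150 days is split by a Day 361 status.* The sentence in 4.2.5.3 refers to LRTI without naming RSV or a window, and neighbouring summaries cover through 150, after 150 and through 360 days.
- *The extra hospital sample alone could give a risk ratio of about 1.3.* That needs the same low positivity at every sample, Day 361 included, which contradicts the late pattern in Phase 1b/2a.

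The default to negative also hardly touches PK, since ADA and PK share a scheduled draw.

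**Conclusion.** Both parts hold on the current text, at modest weight. The incidence denominator is wrong in kind but small in effect: a relative reduction equal to the share of children with only a baseline result, at most about 1 percentage point at 5.6% and about 6 points at 28.2% over the assumed 4% to 20% range. The timing problem matters more for interpretation. On the sponsor's earlier infant data, an assumed Day 151 ratio of 0.50 would show as about 0.93 to 0.80, so a PK table by ever-positive status could look reassuring with a real effect present. This rests on the timing of positives in those studies carrying over to immunocompromised children, and on the inference from the Phase 2b anti-YTE counts. For adverse events and LRTI, the status ignores event order, but no direction or size of bias can be claimed. No error rate or sample size is affected.

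**What to change.** - **Prevalence:** keep the any-result denominator.
- **Incidence and all treatment-emergent categories:** use children with a baseline and at least one post-baseline ADA result, report how many are excluded and why, and require a negative baseline in one consistent wording for induced, persistent and transient ADA.
- **PK by ADA status:** at each visit, classify by ADA results up to and including that visit. Keep the ever-positive split as supplementary.
- **Events:** list each ADA-positive child with the date of first positive relative to each LRTI event or TESAE. Show children with no post-baseline ADA result separately, not as ADA negative. State the event window for the LRTI split.

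The cost is SAP wording and reprogramming before the final lock; no new data are needed. The drawback is sparse cells: with 6% to 17% chance of three early positives in a dose group of 50, and 28% to 54% in all 100, many by-visit summaries may not be calculable and the dated listing may have to serve.

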4.3.6 Estimate of Volume of Blood to be Collected

Blood volume estimates are provided in [Table 7](#) by visit/study day. For all subjects hospitalized with LRTI or any respiratory infection, an additional blood sample will be collected within 2 days following hospital admission.

Table 7 Volume of Blood to be Collected

Visit/Study Day	Estimated Blood Volume
Visit 1/Screening or Visit 2/Day 1	1.5 mL
Visit 3/Day 31	1.5 mL
Visit 5/Day 151	1.5 mL
Visit 6/Day 361	1.5 mL
Total	6.0 mL

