#### **3.1.1      Treatment-emergent adverse events and serious treatment-emergent adverse events (TEAEs and TESAEs)**

Treatment-emergent adverse events are defined as AEs whose onset occurs after receiving nirsevimab and within 360 days post dose. Adverse events with completely missing onset dates and a stop date after the start date of receiving nirsevimab (or unknown stop date) will also be considered treatment emergent. A TESAE is an TEAE which is serious.

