### 4.1 General principles

There are 2 planned analyses for this study: an interim analysis and a final analysis. The interim analysis will be conducted when subjects enrolled globally by the end of 2021 have been followed through Day 151. The final analysis will be conducted when all subjects have completed the last visit of the study (Day 361). The data will be validated as defined in the Data Management Plan.

- For the visit-based summaries for PK/ADA, CCI and clinical laboratory data, the summaries will be based on the scheduled visits using adjusted analysis-defined visit windows. The adjusted analysis-defined windows will be based on the collection schedule listed in the CSP and summaries will be windowed to the closest scheduled visit for those data. Visit windows have been constructed so that every observation collected can be allocated to a particular visit. All data will be included in the listings. If multiple readings are recorded within a single analysis-defined visit window, the following rules will apply: If there are 2 or more valid, non-missing observations within the same visit window, and
  - if they are on different days, then the non-missing one which is closest to the scheduled visit day will be used in the analysis.
  - if they are on the same day which is closest to the scheduled visit day, then the non-missing one with the later collection time will be used in the analysis.
- If 2 or more valid observations are equidistant from the scheduled visit, and
  - if they are on different days, then the non-missing post-dose observation with the earlier collection date will be used in the analysis for the post-baseline observations, and the non-missing pre-dose observation with the later collection date will be used in the analysis for the screening observations.
  - if they are on the same day, then the non-missing observation with the later collection time will be used in the analysis.
- For LRTI visits or unscheduled visits, if 2 or more valid observations are collected on the same day, then the non-missing observation with the later collection time will be included in the analysis.
- If a visit window does not contain any observations, then the data will remain missing.
- For the visit-based summaries for ADA, if both ADA positive and negative samples are available within a subject's visit, ADA positive will be reported.

- For summary Statistics of PK data following rules apply:

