#### **4.1.3 Derivation of study day**

Study day will be calculated as follows:

- If the evaluation date is on or after the administration date of nirsevimab:

study day = date of evaluation – administration date of nirsevimab + 1

- If the evaluation date is before the administration date of nirsevimab:  
study day = date of evaluation – administration date of nirsevimab

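### The ADA-impact tables stop counting positives at 360 days post dose (Day 361), but the last ADA sample may be drawn on schedule up to Day 368 and the SAP's other ADA rules count it

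*SAP*

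**What the plan says.** **ADA status in the impact tables.** SAP 4.2.5.2 summarizes TEAEs and TESAEs by post-baseline ADA status, defined as "ie, at least one post-baseline ADA positive or not through 360 days post dose". The last paragraph of SAP 4.2.5.3 carries the same 360-day definition into the efficacy table: "MA LRTI and MA LRTI with hospitalization will be summarized by ADA post-baseline status (ie, at least one post-baseline ADA positive or not through 360" (the quote stops just before the unit). In both places the time limit stands inside the bracket that defines status.

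**Study day.** SAP 4.1.3, on or after dosing: "study day = date of evaluation – administration date of nirsevimab + 1".

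**Last ADA sample.** Protocol Table 5 schedules the final visit at Day 361 with a tolerance of 7 days either way. Protocol Table 7 lists a blood draw at "Visit 6/Day 361".

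**The other ADA rules in the SAP.**
- 4.2.5.2, ADA positive: "A subject is defined as being ADA positive if a positive ADA result is available at any time, including baseline and all post-baseline measurements". The ADA-by-PK summary in 4.2.5.1 relies on the ADA status definitions given in the ADA section.
- 4.2.5.2, ADA incidence: "Treatment-emergent ADA defined as the sum of both treatment-induced and treatment-boosted ADA". No upper day is given.
- Appendix 2: every ADA sample from Day 256 onward is assigned to the Day 361 visit.
- 4.1: "Visit windows have been constructed so that every observation collected can be allocated to a particular visit".

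**The concern.** One set of rules counts an ADA sample whenever it was drawn. The other, used only for the safety and efficacy impact tables, stops at a day in the middle of the permitted window for the final visit. A sample taken a few days after the target, within tolerance and with no deviation, can therefore be positive in one table and not count in another.

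The final visit is the one where this matters. In the Phase 1b/2a infant study (Protocol 1.4), 18 of the 20 ADA-positive nirsevimab recipients were positive at Day 361 only. Moving such children into the ADA-negative column makes a small positive group smaller. If they resemble the other positives, it also dilutes whatever contrast exists. Protocol 4.8.5 names the association of ADA with TEAEs and TESAEs as something to be assessed if data permit, so the classification behind it should be unambiguous.

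**Working it through.** The plan gives no figure to reproduce. The check is date arithmetic, followed by an illustration of size.

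**1. The limit as a study day.** The dosing day is Day 1, so study day = days post dose + 1. Then 360 + 1 = Day 361.

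**2. The permitted days for the last sample.** 361 − 7 = 354 and 361 + 7 = 368, which is 15 days. Days 362 to 368 are 361 to 367 days post dose and so fall beyond the limit. That is 7 of 15 days, or 46.7%.

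**3. One child followed through the rules.** Take a child who is baseline negative, with a single positive sample on Day 365 (364 days post dose).

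| SAP rule | Status |
|---|---|
| Any-time ADA positive (prevalence, ADA-by-PK) | Positive |
| Treatment-induced, hence ADA incidence | Positive |
| Appendix 2 visit | Day 361 (Day 256 or later) |
| Persistently positive (positive at last available assessment) | Yes |
| Safety impact table, read literally | Negative |
| Efficacy impact table, read literally | Negative |

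The persistently-positive row and the safety-table row both come from 4.2.5.2. A child who was positive at baseline would still be positive for prevalence and PK, but would enter incidence only with a titer boost of at least 4-fold.

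**4. Size.** Children reclassified per 100 = 100 × (proportion positive only at the last visit) × (share of last visits after Day 361). The documents give no visit-timing data, so the second factor is assumed. Two sources in Protocol 1.4 give the first factor:
- Phase 1b/2a: 18/68 = 26.5% positive at Day 361 only.
- Phase 2b: at most 30/929 = 3.2%. The 30 is the number of post-baseline-positive subjects in the Day 361 anti-YTE result. The text does not say they were positive only then, so this is an upper limit.

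| Assumed share of last visits after Day 361 | Phase 1b/2a rate, per 100 | Phase 2b rate (maximum), per 100 |
|---|---|---|
| 0% | 0 | 0 |
| 25% | 6.6 | 0.8 |
| 46.7% (even spread) | 12.4 | 1.5 |
| 75% | 19.9 | 2.4 |
| 100% | 26.5 | 3.2 |

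With about 100 subjects planned, these are roughly numbers of children in this trial, if its ADA rate resembles one of those studies and every child gives a last sample.

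**The case against.** The best reply is that the nominal visit was meant. Protocol 3.2.3 describes ADA sampling as running to 360 days after dosing, although Table 5 of the same protocol lets the last draw fall on Day 368. The authors may thus have used 360 days as shorthand for the Day 361 visit, and Appendix 2 would then place a Day 365 sample in that visit. On this reading no child is reclassified. The reading is plausible, but the SAP does not state it. Where the SAP applies the same period to adverse events it is an actual-day cut: TEAEs are "AEs whose onset occurs after receiving nirsevimab and within 360 days post dose", and 4.2.4.1 treats events after Day 361 as not treatment-emergent. A programmer could fairly code either version.

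A second reply is that ending ADA ascertainment when event counting ends is a reasonable choice. It could be, but the SAP gives no such reason. The cut also does not put ADA before events in time, because a positive on Days 354 to 361 counts against everything that preceded it.

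A third reply is that little depends on the point. SAP section 4 plans no formal comparisons. ADA-positive counts can also differ between tables by design, since prevalence, incidence and post-baseline status are different quantities. This stands: unequal counts alone would not show an error.

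A reader might go further and infer that about 42% of ADA-positive children will be mislabelled (0.467 × 18/20) and the ADA contrast materially biased. The documents do not support that. The figure needs the literal reading, evenly spread visits and the pattern of one 71-infant study. In the far larger Phase 2b study 52 of 929 subjects (5.6%) were ADA positive, and at most 30 of those 52 could have been positive only at Day 361. No event rates by ADA status are given from which a bias could be calculated.

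**Conclusion.** The conflict in the wording is real. Taken literally, SAP 4.2.5.2 and 4.2.5.3 classify an on-schedule positive on Days 362 to 368 as negative in the two impact tables, while the rest of the SAP counts it. Only children with no other post-baseline positive are affected.

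The size is uncertain: about 12 per 100 at the Phase 1b/2a rate and at most about 1.5 per 100 at the Phase 2b rate, both assuming evenly spread last visits, and none if the nominal visit was intended. No error rate, power or primary conclusion depends on it. It is worth correcting because the rule as written can misclassify children and the remedy is very cheap.

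**What to change.** In SAP 4.2.5.2 and 4.2.5.3, state that post-baseline ADA status is based on all post-baseline samples, including every sample that Appendix 2 maps to the Day 361 window (Day 256 or later).

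State separately that the 360-day limit applies to the events counted: TEAEs and TESAEs in the safety table, MA LRTI and MA LRTI with hospitalization in the efficacy table. Deleting the time phrase is not enough in 4.2.5.3. It is the only period in the ADA-by-efficacy sentence, and the nearby sentence setting reporting periods refers to the summaries above it. The event period must therefore be written in.

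If the nominal visit was always meant, the same wording records that. The cost is a sentence or two of SAP text in two places, with no new data and no change to study conduct.
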